### 5.2.2 Timing of Dose Administration

Trial treatment should be administered on Day 1 of each cycle after all procedures/assessments have been completed as detailed on the Trial Flow Chart (Section 6.0). Trial treatment may be administered up to 3 days before or after the scheduled Day 1 of each cycle due to administrative reasons.

All trial treatments will be administered on an outpatient basis.

Pembrolizumab 200 mg will be administered as a 30 minute IV infusion every  $21 \pm 3$  days. Every effort should be made to target infusion timing to be as close to 30 minutes as possible. However, given the variability of infusion pumps, a window of -5 minutes and +10 minutes is permitted (i.e., infusion time is 30 minutes: -5 min/+10 min).

The Pharmacy Manual contains specific instructions for the preparation of the pembrolizumab infusion fluid and administration of infusion solution.

### 5.2.3 Trial Blinding/Masking

This is an open-label trial; therefore, the study team, investigator and subject will know the treatment administered.

### 5.3 Randomization or Treatment Allocation

There will not be any randomization. All subjects will receive the same treatment.

### 5.4 Stratification

There will not be any formal stratification.

9458- Protocol Version Date 28 Feb 2019

## **5.5 Concomitant Medications/Vaccinations (allowed & prohibited)**

Medications or vaccinations specifically prohibited in the exclusion criteria are not allowed during the ongoing trial. If there is a clinical indication for one of these or other medications or vaccinations specifically prohibited during the trial, discontinuation from trial therapy may be required. The investigator should discuss any questions regarding this with the Merck Clinical team. The final decision on any supportive therapy or vaccination rests with the investigator and/or the subject's primary physician.

### **5.5.1 Acceptable Concomitant Medications**

All treatments that the investigator considers necessary for a subject's welfare may be administered at the discretion of the investigator in keeping with the community standards of medical care. All concomitant medication will be recorded on the case report form (CRF) including all prescription, over-the-counter (OTC), herbal supplements, and IV medications and fluids. If changes occur during the trial period, documentation of drug dosage, frequency, route, and date may also be included on the CRF.

All concomitant medications received within 28 days before the first dose of trial treatment and 30 days after the last dose of trial treatment should be recorded. Concomitant medications administered after 30 days after the last dose of trial treatment should be recorded for SAEs and events of clinical interest (ECIs) as defined in Section 7.2.

### **5.5.2 Prohibited Concomitant Medications**

Subjects are prohibited from receiving the following therapies during the Screening and Treatment Phase (including retreatment for post-complete response relapse) of this trial:

- Antineoplastic systemic chemotherapy or biological therapy
- Immunotherapy not specified in this protocol
- Chemotherapy not specified in this protocol
- Investigational agents other than pembrolizumab
- Radiation therapy
- Live vaccines within 30 days prior to the first dose of trial treatment and while participating in the trial. Examples of live vaccines include, but are not limited to, the following: measles, mumps, rubella, varicella/zoster, yellow fever, rabies, BCG, and typhoid vaccine.
- Systemic glucocorticoids for any purpose other than to modulate symptoms from an event of clinical interest of suspected immunologic etiology. The use of physiologic doses of corticosteroids may be approved after consultation with the PI.

Subjects who enroll in the context of persistent MRD following prior treatment will not be allowed to continue this prior treatment. Subjects who, in the assessment by the investigator, require the use of any of the aforementioned treatments for clinical management should be

9458- Protocol Version Date 28 Feb 2019

removed from the trial. Subjects may receive other medications that the investigator deems to be medically necessary.

The Exclusion Criteria describes other medications which are prohibited in this trial.

There are no prohibited therapies during the Post-Treatment Follow-up Phase.

## **5.6 Rescue Medications & Supportive Care**

### **5.6.1 Supportive Care Guidelines**

Subjects should receive appropriate supportive care measures as deemed necessary by the treating investigator. Suggested supportive care measures for the management of adverse events with potential immunologic etiology are outlined below. Where appropriate, these guidelines include the use of oral or intravenous treatment with corticosteroids as well as additional anti-inflammatory agents if symptoms do not improve with administration of corticosteroids. Note that several courses of steroid tapering may be necessary as symptoms may worsen when the steroid dose is decreased. For each disorder, attempts should be made to rule out other causes such as relapsed disease or bacterial or viral infection, which might require additional supportive care. The treatment guidelines are intended to be applied when the investigator determines the events to be related to pembrolizumab.

Note: if after the evaluation the event is determined not to be related, the investigator is instructed to follow the ECI reporting policies but does not need to follow the treatment guidance. Refer to Section 5.2.1 for dose modification.

It may be necessary to perform conditional procedures such as bronchoscopy, endoscopy, or skin photography as part of evaluation of the event.

- **Pneumonitis:**

- For **Grade 2 events**, treat with systemic corticosteroids. When symptoms improve to Grade 1 or less, steroid taper should be started and continued over no less than 4 weeks.
- For **Grade 3-4 events**, immediately treat with intravenous steroids. Administer additional anti-inflammatory measures, as needed.
- Add prophylactic antibiotics for opportunistic infections in the case of prolonged steroid administration.

- **Diarrhea/Colitis:**

Subjects should be carefully monitored for signs and symptoms of enterocolitis (such as diarrhea, abdominal pain, blood or mucus in stool, with or without fever) and of bowel perforation (such as peritoneal signs and ileus).

- All subjects who experience diarrhea/colitis should be advised to drink liberal quantities of clear fluids. If sufficient oral fluid intake is not feasible, fluid and electrolytes should be substituted via IV infusion. For Grade 2 or higher diarrhea, consider GI consultation and endoscopy to confirm or rule out colitis.

9458- Protocol Version Date 28 Feb 2019

- For **Grade 2 diarrhea/colitis** that persists greater than 3 days, administer oral corticosteroids.
- For **Grade 3 or 4 diarrhea/colitis** that persists > 1 week, treat with intravenous steroids followed by high dose oral steroids.
- When symptoms improve to Grade 1 or less, steroid taper should be started and continued over no less than 4 weeks.
  
- **Type 1 diabetes mellitus (if new onset, including diabetic ketoacidosis [DKA]) or ≥ Grade 3 Hyperglycemia, if associated with ketosis (ketonuria) or metabolic acidosis (DKA)**
  - For **T1DM or Grade 3-4 Hyperglycemia**
    - Insulin replacement therapy is recommended for Type I diabetes mellitus and for Grade 3-4 hyperglycemia associated with metabolic acidosis or ketonuria.
    - Evaluate patients with serum glucose and a metabolic panel, urine ketones, glycosylated hemoglobin, and C-peptide.
  
- **Hypophysitis:**
  - For **Grade 2** events, treat with corticosteroids. When symptoms improve to Grade 1 or less, steroid taper should be started and continued over no less than 4 weeks. Replacement of appropriate hormones may be required as the steroid dose is tapered.
  - For **Grade 3-4** events, treat with an initial dose of IV corticosteroids followed by oral corticosteroids. When symptoms improve to Grade 1 or less, steroid taper should be started and continued over no less than 4 weeks. Replacement of appropriate hormones may be required as the steroid dose is tapered.
  
- **Hyperthyroidism or Hypothyroidism:**

Thyroid disorders can occur at any time during treatment. Monitor patients for changes in thyroid function (at the start of treatment, periodically during treatment, and as indicated based on clinical evaluation) and for clinical signs and symptoms of thyroid disorders.

  - **Grade 2 hyperthyroidism events (and Grade 2-4 hypothyroidism):**
    - In hyperthyroidism, non-selective beta-blockers (e.g. propranolol) are suggested as initial therapy.
    - In hypothyroidism, thyroid hormone replacement therapy, with levothyroxine or liothyronine, is indicated per standard of care.
  - **Grade 3-4 hyperthyroidism**
    - Treat with an initial dose of IV corticosteroid followed by oral corticosteroids. When symptoms improve to Grade 1 or less, steroid taper should be started and continued over no less than 4 weeks. Replacement of appropriate hormones may be required as the steroid dose is tapered.

- **Hepatic:**
  - For **Grade 2** events, monitor liver function tests more frequently until returned to baseline values (consider weekly).
    - Treat with IV or oral corticosteroids
  - For **Grade 3-4** events, treat with intravenous corticosteroids for 24 to 48 hours.
  - When symptoms improve to Grade 1 or less, a steroid taper should be started and continued over no less than 4 weeks.
  
- **Renal Failure or Nephritis:**
  - For **Grade 2** events, treat with corticosteroids.
  - For **Grade 3-4** events, treat with systemic corticosteroids.
  - When symptoms improve to Grade 1 or less, steroid taper should be started and continued over no less than 4 weeks.
  
- **Management of Complications Unique to HCT or Cellular Immunotherapy:** A potential risk of administering pembrolizumab to patients who have previously received HCT or other cellular immunotherapy modalities like CAR-T cells is a recrudescence of toxicities that are germane to these specific therapies, including GVHD, cytokine release syndrome (CRS), and neurologic toxicity. The manifestations of such events (e.g., diarrhea, pneumonitis, rash, hepatitis, etc.) are included in the specific guidelines above. As needed and on a case-by-case basis, best local practices and additional expert consultation can also be instituted as needed for management of these toxicities, should they develop. Recording and reporting of these adverse events will follow the same guidelines as those set out elsewhere in the protocol (Section 7.2).
  
- **Management of Infusion Reactions:** Signs and symptoms usually develop during or shortly after drug infusion and generally resolve completely within 24 hours of completion of infusion.

Minor deviations from these guidelines will be permitted, at the discretion of the treating investigator.

Table 4 below shows treatment guidelines for subjects who experience an infusion reaction associated with administration of pembrolizumab (MK-3475). Minor deviations from these guidelines will be permitted, at the discretion of the treating investigator.

Table 4 Infusion Reaction Treatment Guidelines

NCI CTCAE Grade	Treatment	Premedication at subsequent dosing
Grade 1 Mild reaction; infusion interruption not indicated; intervention not indicated	Increase monitoring of vital signs as medically indicated until the subject is deemed medically stable in the opinion of the investigator.	None

9458- Protocol Version Date 28 Feb 2019

NCI CTCAE Grade	Treatment	Premedication at subsequent dosing

Grade 2 Requires therapy or infusion interruption but responds promptly to symptomatic treatment (e.g., antihistamines, NSAIDS, narcotics, IV fluids); prophylactic medications indicated for <=24 hrs
	
Stop Infusion and monitor symptoms. Additional appropriate medical therapy may include but is not limited to: IV fluids Antihistamines NSAIDS Acetaminophen Narcotics
 
Increase monitoring of vital signs as medically indicated until the subject is deemed medically stable in the opinion of the investigator. If symptoms resolve within one hour of stopping drug infusion, the infusion may be restarted at 50% of the original infusion rate (e.g., from 100 mL/hr to 50 mL/hr). Otherwise dosing will be held until symptoms resolve and the subject should be premedicated for the next scheduled dose.
 
Subjects who develop Grade 2 toxicity despite adequate premedication should be permanently discontinued from further trial treatment administration.
	
Subject may be premedicated 1.5h (± 30 minutes) prior to infusion of pembrolizumab (MK-3475) with:
 
Diphenhydramine 50 mg po (or equivalent dose of antihistamine).
 
Acetaminophen 500-1000 mg po (or equivalent dose of antipyretic).

Grades 3 or 4
 
Grade 3: Prolonged (i.e., not rapidly responsive to symptomatic medication and/or brief interruption of infusion); recurrence of symptoms following initial improvement; hospitalization indicated for other clinical sequelae (e.g., renal impairment, pulmonary infiltrates)
 
Grade 4: Life-threatening; pressor or ventilatory support indicated
	
Stop Infusion. Additional appropriate medical therapy may include but is not limited to: IV fluids Antihistamines NSAIDS Acetaminophen Narcotics Oxygen Pressors Corticosteroids Epinephrine
 
Increase monitoring of vital signs as medically indicated until the subject is deemed medically stable in the opinion of the investigator. Hospitalization may be indicated. Subject is permanently discontinued from further trial treatment administration.
	
No subsequent dosing

Appropriate resuscitation equipment should be available and an adequately-trained medical provider/physician readily available during the period of drug administration.
		

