#### 5.2.1.2 Dose Modification

AEs associated with pembrolizumab exposure may represent an immunologic etiology. These immune-related AEs (irAEs) may occur shortly after the first dose or several months after the last dose of pembrolizumab treatment and may affect more than one body system simultaneously. Therefore, early recognition and initiation of treatment is critical to reduce complications. Based on existing clinical study data, most irAEs were reversible and could be managed with interruptions of pembrolizumab, administration of corticosteroids and/or other supportive care. For suspected irAEs, ensure adequate evaluation to confirm etiology or exclude other causes. Additional procedures or tests such as bronchoscopy, endoscopy, skin biopsy may be included as part of the evaluation. Based on the severity of irAEs, withhold or permanently discontinue pembrolizumab and administer corticosteroids. Dose modification and toxicity management guidelines for irAEs associated with pembrolizumab are provided in Table 3.

Table 3: Dose Modification Guidelines for Drug-Related Adverse Events

General instructions:				

 
1. Corticosteroid taper should be initiated upon AE improving to Grade 1 or less and continue to taper over at least 4 weeks.
 
2. For situations where pembrolizumab has been withheld, pembrolizumab can be resumed after AE has been reduced to Grade 1 or 0 and corticosteroid has been tapered. Pembrolizumab should be permanently discontinued if AE does not resolve within 12 weeks of last dose or corticosteroids cannot be reduced to <math>\leq 10</math> mg prednisone or equivalent per day within 12 weeks.
 
3. For severe and life-threatening irAEs, IV corticosteroid should be initiated first followed by oral steroid. Other immunosuppressive treatment should be initiated if irAEs cannot be controlled by corticosteroids.
 
				
Immune-related AEs	Toxicity grade or conditions (CTCAEv5.0)	Action taken to pembrolizumab	irAE management with corticosteroid and/or other therapies	Monitor and follow-up

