Pneumonitis	Grade 2	Withhold	
 
• Administer corticosteroids (initial dose of 1-2 mg/kg prednisone or equivalent) followed by taper
 
	
 
• Monitor participants for signs and symptoms of pneumonitis
 
• Evaluate participants with suspected pneumonitis with radiographic imaging and initiate corticosteroid treatment
 
• Add prophylactic antibiotics for opportunistic infections
 

	Grade 3 or 4, or recurrent Grade 2	Permanently discontinue		
Diarrhea / Colitis	Grade 2 or 3	Withhold	
 
• Administer corticosteroids (initial dose of 1-2 mg/kg prednisone or equivalent) followed by taper
 
	
 
• Monitor participants for signs and symptoms of enterocolitis (ie, diarrhea, abdominal pain, blood or mucus in stool with or without fever) and of bowel perforation (ie, peritoneal signs and ileus).
 
• Participants with <math>\geq</math> Grade 2 diarrhea suspecting colitis should consider GI consultation and performing endoscopy to rule out colitis.
 
• Participants with diarrhea/colitis should be advised to drink liberal quantities of clear fluids. If sufficient oral fluid intake is not feasible, fluid and electrolytes should be substituted via IV infusion.
 

	Grade 4	Permanently discontinue		
AST / ALT elevation or Increased bilirubin	Grade 2	Withhold	
 
• Administer corticosteroids (initial dose of 0.5- 1 mg/kg prednisone or equivalent) followed by taper
 
	
 
• Monitor with liver function tests (consider weekly or more frequently until liver enzyme value returned to baseline or is stable)
 

	Grade 3 or 4	Permanently discontinue		

9458- Protocol Version Date 28 Feb 2019

			prednisone or equivalent) followed by taper	
Type 1 diabetes mellitus (T1DM) or Hyperglycemia	Newly onset T1DM or Grade 3 or 4 hyperglycemia associated with evidence of $\beta$ -cell failure	Withhold	
 
Initiate insulin replacement therapy for participants with T1DM
 
Administer anti-hyperglycemic in participants with hyperglycemia
 
	
 
Monitor participants for hyperglycemia or other signs and symptoms of diabetes.
 

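### Section 5.6.1 ties IV steroids for Grade 3-4 diarrhea/colitis to more than one week of persistence, a longer threshold than for Grade 2 and in conflict with Table 3

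*Combined protocol and SAP*

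**What the plan says.** Two parts of the protocol direct steroids for immune-related diarrhea/colitis.

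**Section 5.6.1, Supportive Care Guidelines.** The Grade 2 line applies to diarrhea/colitis "that persists greater than 3 days, administer oral corticosteroids". The next line, for Grade 3 or 4, applies to diarrhea/colitis "that persists > 1 week, treat with intravenous steroids followed by high dose oral steroids". The section describes its own status as follows: "Suggested supportive care measures for the management of adverse events with potential immunologic etiology are outlined below". It adds that "The treatment guidelines are intended to be applied when the investigator determines the events to be related to pembrolizumab".

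**Section 5.2.1.2, Dose Modification, with Table 3.** The text says that "Dose modification and toxicity management guidelines for irAEs associated with pembrolizumab are provided in Table 3". The diarrhea/colitis row says "Administer corticosteroids (initial dose of 1-2 mg/kg prednisone or equivalent) followed by taper". General instruction 3 of the table says "For severe and life-threatening irAEs, IV corticosteroid should be initiated first followed by oral steroid". The opening paragraph states the principle that "early recognition and initiation of treatment is critical to reduce complications".

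**The concern.** A steroid threshold would be expected to shorten, or at least not lengthen, as severity rises. Here it lengthens, and no text explains why. A physician who opens Section 5.6.1 to manage a Grade 3 or 4 event finds a one-week trigger and nothing about the days before it. A physician who opens Table 3 finds no wait at all.

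What is at stake is the safety of the individual subject. Section 5.6.1 itself asks for monitoring for signs of bowel perforation in this setting. A reader who follows the printed trigger could hold back IV steroids for more than a week in severe or life-threatening colitis.

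**Working it through.** No sample size, power or error rate is involved. The check sets the texts side by side.

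**1. Thresholds for diarrhea/colitis**

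| Source | Grade 2 | Grade 3-4 |
|---|---|---|
| Section 5.6.1 | oral steroids after > 3 days | IV steroids after > 1 week (> 7 days) |
| Table 3, diarrhea/colitis row | steroids, no persistence condition | steroids, no persistence condition |
| Table 3, general instruction 3 | not addressed | IV steroid first, no waiting period |

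Difference within Section 5.6.1: 7 - 3 = 4 days longer for the more severe grades.

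**2. Does general instruction 3 reach both grades?** Yes. Table 6 describes Grade 3 as severe, and Grade 4 as life-threatening with urgent intervention indicated. In the text as extracted, the steroid cell of the Table 3 row is printed beside Grade 2 or 3. Even if that cell were read as leaving out Grade 4, general instruction 3 would still cover it.

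**3. Is a persistence condition the pattern in Section 5.6.1?** These are the Grade 3-4 lines that direct steroids:

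| Disorder | Steroid named | Persistence condition |
|---|---|---|
| Pneumonitis | IV, immediately | none |
| Diarrhea/colitis | IV, then oral | > 1 week |
| Hypophysitis | IV, then oral | none |
| Hyperthyroidism | IV, then oral | none |
| Hepatic | IV | none |
| Renal | systemic, route not given | none |

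The diabetes/hyperglycemia line names insulin rather than steroids and is not counted. That gives six lines: one with a condition and 6 - 1 = 5 without. Of those five, four name IV steroids and the renal line says systemic.

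**4. Who would meet the full wait?** A subject whose diarrhea/colitis was at Grade 2 for more than 3 days before worsening already met the oral-steroid line. The full week therefore applies mainly to abrupt onset at Grade 3 or 4.

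**The case against.** The strongest reply is that nothing in Section 5.6.1 stops a physician from treating at once. The guidance is labelled as suggested. Section 5.5 leaves the final decision on supportive therapy with the investigator and/or the primary physician. A sentence after the list of disorders permits minor deviations at the treating investigator's discretion, although its scope is arguable because it follows the infusion-reaction item. Table 3 is the named guideline for toxicity management, and Section 5.6.1 points back to Section 5.2.1 for dose modification. A physician who starts IV steroids at onset follows Table 3 and breaches nothing.

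All of that stands, and it limits the harm. A reader might infer that the protocol withholds steroids, or allows them only after a week. The documents do not support that: the line is silent about the first week, and Table 3 fills the silence. Nor does any text tie the point to the primary endpoint or to who stays on treatment.

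The reply does not reconcile the two texts. The pointer to Section 5.2.1 concerns dose modification, and no clause says which text decides steroid timing.

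A second reply is that the week allows time for work-up, since the section asks for infection and other causes to be ruled out. Days of diarrhea before attribution can count toward the week, so the wait need not start when the event is judged related. But the request to rule out other causes applies to every disorder listed, and no other Grade 3-4 steroid line has a wait. An event judged related early would still fall short of the printed trigger until more than 7 days had passed.

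**Conclusion.** The concern holds as an inconsistency in safety guidance. For Grade 3-4 diarrhea/colitis, Section 5.6.1 states a steroid trigger that is longer than its own Grade 2 trigger, has no counterpart in the other five Grade 3-4 steroid lines, and conflicts with Table 3 and general instruction 3. The risk is delayed IV steroids by a reader who relies on Section 5.6.1 alone, mainly in abrupt Grade 3-4 onset.

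The size is > 7 days against > 3 days within Section 5.6.1, and against no stated wait in Table 3. How many subjects this could affect is unknown, because the documents give no colitis rate. The conclusion rests on reading severe and life-threatening in general instruction 3 as Grades 3 and 4, which Table 6 supports. The two-stage design, its error rates and the early-relapse stopping rule are untouched. The correction should be made because it costs almost nothing and bears on subject safety.

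**What to change.** In Section 5.6.1, delete the one-week persistence clause from the Grade 3 or 4 diarrhea/colitis line. The line then directs intravenous steroids, followed by high-dose oral steroids, for any Grade 3 or 4 event to which the guidance applies. That agrees with general instruction 3.

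Do not add a general sentence that Table 3 prevails wherever the two differ. Table 3 has no persistence condition for Grade 2 diarrhea/colitis either, so the sentence would also cancel the three-day Grade 2 condition. For hyperthyroidism, the Table 3 row names beta-blockers or thionamides, whereas Section 5.6.1 directs steroids at Grade 3-4. A blanket rule could remove that instruction or set the row against general instruction 3.

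The cost is one clause of protocol wording, with no new procedures, visits or data.
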